6.2.2 Treatment period(s)

Treatment phase will be a 24 week period, beginning at visit 2.

Visits are planned after 3, 6, 12, 18 and 24 weeks after randomization. If additional time is needed after randomization to schedule the pulmonary rehabilitation for a patient randomized to that group, the time between visits 2 and 3 may be extended up to 6 weeks. The visit schedule will resume on the day of the first pulmonary rehabilitation visit, and all subsequent visits will be scheduled accordingly to keep the time between visits per protocol and a total 24 week treatment period.

During all the visits it is important that patients' questionnaires are completed before any other procedure. The order of the other procedures to be followed is given below as an indication but can be adapted for practical reasons.

Visit 2

- SGRQ, KBILD and UCSD SOBQ
- Adverse events and concomitant therapy assessment since last visit
- Download/review PROactive Tool and activity monitor results
- Physical examination including vital signs
- Resting SpO₂
- Blood samples for laboratory tests
- Urinary pregnancy test
- Pulmonary function test including FVC
- DL_{CO}
- Assessment of in/exclusion criteria
- Randomisation via IRT
- 6 minute walk test
- [REDACTED]
- Schedule patient for pulmonary rehabilitation if randomized to that treatment group
- Schedule Visit 3
- Send HRCT for calculation of QLF if not previously available.

Visits 3, 4, 5 and 6:

- Adverse events and concomitant therapy assessment since last visit
- Collect and download/review PROActive Tool from eDiary and activity monitor data at Visit 5
- Review pulmonary rehabilitation attendance with patient and record information from pulmonary rehabilitation reports into eCRF for patients in the PR treatment group at Visits 3, 4 and 5
- Physical examination including vital signs
- Blood samples for laboratory tests
- Urinary pregnancy test
- SGRQ, KBILD and UCSD SOBQ at Visit 5
- Pulmonary function test including FVC at Visit 5
- DLCO at Visit 5
- SP02 at Visit 5
- Six minute walk test at Visit 5
- [REDACTED]
- Instruct patient on activity monitoring and eDiary (or eDiary application for own device) and remind patient they need to pick up or will receive device in the mail to allow 7 days of use prior to next visit at Visits 4 and 6
- Schedule next visit.

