6.2.3 Follow up period and trial completion

- Visit 7/End of Treatment (EOT) or when the patient is discontinued
- Adverse events and concomitant therapy assessment since last visit

- Review pulmonary rehabilitation attendance with patient and record information from pulmonary rehabilitation reports into eCRF for patients in the PR treatment group (for patients discontinued during first 12 weeks)
- Physical examination including vital signs
- SGRQ, KBILD and UCSD SOBQ
- Collect and download/review PROActive Tool from eDiary and activity monitor data
- Resting SpO₂
- Resting 12-lead electrocardiogram
- Blood samples for laboratory tests
- Urinary pregnancy test (done locally)
- Pulmonary function test including FVC
- DL_{CO}
- Six minute walk test
- 
- End Of Treatment page to be completed

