7. PLANNED ANALYSIS

For End-Of-Text (EoT) tables, the set of summary statistics is: N / Mean / SD / Min / Median / Max. In descriptive statistics tables, mean and median will be rounded to one additional digit than the raw individual value. SD will be rounded to one additional digit than the mean.

For tables that are provided for endpoints with some extreme data, median, quartiles and percentiles should be preferred to mean, standard deviation, minimum and maximum.

Tabulations of frequencies for categorical data will include all possible categories and will display the number of observations in a category as well as the percentage (%) relative to the respective treatment group (unless otherwise specified, all subjects in the respective subject set whether they have non-missing values or not).

The precision for percentages should be one decimal point, unless the denominator is smaller than 100 (in all treatment columns), in which case percentages are given in integer numbers. The category missing will be displayed only if there are actually missing values.

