7.7 EXTENT OF EXPOSURE

The data will be analysed on the RS. A summary table showing the duration on pulmonary rehabilitation (both mean and frequency, see Section 5.4.3).

A table displaying the disposition of patients and the conclusion of patients' participation, and a table displaying the primary reason for non-inclusion/randomization will be provided.

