7.8.1 Adverse Events

The analyses of AEs will be descriptive in nature and will be based on BI standards (11). No hypothesis testing is planned. All analyses of AEs will be based on the number of subjects with AEs and NOT on the number of AEs.

For analysis, multiple AE occurrence data on the CRF will be collapsed into an AE event provided that all of the following applies:

- All AE attributes are identical (LLT, intensity, action taken, therapy required, seriousness, reason for seriousness, relationship [investigator defined drug-relatedness], outcome, AE of special interest)
- The occurrences were time-overlapping or time-adjacent (time-adjacency of 2 occurrences is given if the second occurrence started on the same day or on the day after the end of the first occurrence)

For further details on summarization of AE data, please refer to the guideline "Analysis and Presentation of Adverse Event Data from Clinical Trials" (11).

The analysis of adverse events will be based on the concept of treatment emergent adverse events. That means that all adverse events occurring between first nintedanib intake on/after randomization till 28 days after last nintedanib intake will be assigned to the treatment period. All adverse events occurring before first nintedanib intake will be assigned to 'screening' or 'post-randomisation' and all adverse events occurring after last nintedanib intake will be assigned to 'residual effect', 'post-treatment' or 'post-study' (for listings only). Also, all adverse events occurring between the start of an interruption and the end of interruption will be assigned to 'off-treatment' period in the listings. For details on the treatment definition, see Section 6.1.

According to ICH E3 (10), AEs classified as 'other significant' needs to be reported and will include those non-serious and non-significant AEs with (i) 'action taken = discontinuation' or 'action taken = reduced', or (ii) marked haematological and other lab abnormalities or lead to

significant concomitant therapy as identified by the Clinical Monitor/Investigator at a MQRM.

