An overall summary of adverse events will be presented. The frequency of subjects with AEs will be summarised by treatment, primary system organ class and PT (mention MedDRA levels to be displayed in the tables). Separate tables will be provided for subjects with other significant adverse events according to ICH E3 (10), for subjects with significant non-serious adverse events (only if these are defined for the project) and for subjects with serious adverse events (SAEs).

The system organ classes will be sorted by default alphabetically, PTs will be sorted by frequency (within SOC). Customized sorting orders may also be used based on trial needs, e.g. SOC sorted by frequency.

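### SAE and AESI percentages by arm ignore observation time, although only rehabilitation patients can have their schedule extended, and protocol and SAP start the safety window differently

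*SAP*

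**What the plan says.** SAP 7.8 restricts the adverse event analysis to serious events and events of special interest, and says it follows the protocol. SAP 7.8.1 sets the counting rule: "All analyses of AEs will be based on the number of subjects with AEs and NOT on the number of AEs". It then specifies the tables: "The frequency of subjects with AEs will be summarised by treatment, primary system organ class and PT". Under the general rules in SAP 7, such counts are shown with "the percentage (%) relative to the respective treatment group". The extent-of-exposure section (SAP 7.7) offers only this: "A summary table showing the duration on pulmonary rehabilitation (both mean and frequency, see Section 5.4.3". Controls have no such duration.

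On the window, SAP 7.8.1 states that "all adverse events occurring between first nintedanib intake on/after randomization till 28 days after last nintedanib intake will be assigned to the treatment period". SAP 6.1 defines the safety periods on the same nintedanib basis. Protocol 7.3.4 is different: its on-treatment period runs from the start of rehabilitation to the end of the trial.

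On the schedule, Protocol 6.2.2 allows that, for a patient assigned to rehabilitation who needs more time for scheduling, "the time between visits 2 and 3 may be extended up to 6 weeks". After that, "all subsequent visits will be scheduled accordingly to keep the time between visits per protocol and a total 24 week treatment period". Footnote 6 of the flow chart agrees: the treatment period begins on the first rehabilitation day and the visits shift with it. Events are collected from consent to the end of the study (Protocol 5.2.6.2), and there is no follow-up after Visit 7 (Protocol 6.1). The final visit in Protocol 6.2.3 is headed "Visit 7/End of Treatment (EOT) or when the patient is discontinued".

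**The concern.** The percentage of subjects with an event compares arms fairly when both are watched for about the same time. Here Visit 7 can move later in one arm only, and under the SAP window the scheduling delay counts as time at risk. With identical true risk, delayed starts would therefore raise the SAE percentage in the rehabilitation arm. The bias has a known direction, and a confidence interval would not reveal it.

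The planned tables would not let a reader correct for this, because observation time is not summarised by arm. Laboratory and ECG analyses are not planned (Protocol 7.3.4; SAP 7.8.2 and 7.8.4), so the SAE and AESI tables carry much of what will be said about harms.

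The size of the bias also depends on which document's window is programmed, and the two disagree.

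**Working it through.** The plan states no SAE rate and no precision figure for harms, so there is no figure of its own to reproduce. All event risks below are assumptions, shown over a range.

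**Inputs.** Follow-up after the start of the treatment period: 24 weeks (Protocol 6.2.2). Scheduling allowance, rehabilitation arm only: up to 6 weeks (Protocol 6.2.2; flow chart footnote 6). Planned size: 145 per arm (Protocol 3.1).

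**Step 1: maximum time at risk after randomisation, SAP window.**
- If 6 weeks is added to the usual interval: 24 + 6 = 30 weeks; ratio 30/24 = 1.25.
- If 6 weeks is the whole Visit 2 to 3 interval, normally 3 weeks: the delay is 6 − 3 = 3 weeks; 24 + 3 = 27 weeks; ratio 27/24 = 1.125.
- Control: 24 weeks.

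**Step 2: effect on the percentage with equal risk.** Let r be the 24-week risk and d the delay in weeks. With a constant hazard h = −ln(1 − r)/24, the observed percentage is 1 − exp(−h(24 + d)) = 1 − (1 − r)^((24 + d)/24). For r = 20%: 1 − 0.8^1.125 = 22.2% and 1 − 0.8^1.25 = 24.3%. The last column averages the formula over delays spread evenly from 0 to 6 weeks.

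| Assumed 24-week risk (controls) | All delayed 3 weeks | All delayed 6 weeks | Delays spread over 0–6 weeks |
|---|---|---|---|
| 5% | 5.6% | 6.2% | 5.6% |
| 10% | 11.2% | 12.3% | 11.2% |
| 20% | 22.2% | 24.3% | 22.2% |
| 30% | 33.1% | 36.0% | 33.0% |

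The risk ratio is 1.20 to 1.24 if everyone has the 6-week delay, and 1.10 to 1.12 if delays are spread evenly.

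**Step 3: comparison with sampling error.** The 95% half-width for the difference is 1.96 × √(p₁(1 − p₁)/145 + p₂(1 − p₂)/145). For 20% and 24.3% this is 1.96 × 0.0487 = 9.5 points, against a shift of 4.3 points. For 10% and 12.3% it is 7.2 points, against 2.3.

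**Step 4: what person-time would show.** If a subject's time stops at the first event, expected events divided by expected time is [1 − exp(−hT)] / {[1 − exp(−hT)]/h} = h for any follow-up length T. The rate ratio is 1.00 with or without a delay. The percentage with an event by a fixed day after randomisation is likewise equal in both arms under this model.

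**Step 5: the windows side by side.**
- SAP 6.1 and 7.8.1: starts at nintedanib intake on or after randomisation. The delay counts, and both arms have a start.
- Protocol 7.3.4: starts at rehabilitation. The delay does not count, and controls have no start.
- SAP 7.8: says the analysis is as the protocol defines it.

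SAP 4 records that the trial periods were deliberately separated for efficacy and safety, so the nintedanib-based window looks intended. The statement in SAP 7.8 nevertheless contradicts it.

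**The case against.** Several points on the other side stand in whole or in part.

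- **Protocol 7.3.4 leaves out the delay.** If that window were used, with controls started at randomisation, this imbalance would largely disappear. But the protocol gives controls no start, and the SAP's detailed rule is different. This is a reason to reconcile the documents; it does not settle which window will be programmed.
- **The rule on counting subjects does not exclude rates.** A reader might take it as a ban on person-time. It rules out counting events; subjects with a first event per patient-year would comply. That person-time is missing is inferred from SAP 7, 7.7 and 7.8.1 together. SAP 7.8.1 also refers to a sponsor guideline for further detail, and that guideline cannot be checked here.
- **A reader might infer that the rehabilitation arm is observed 25% longer.** The documents do not support that. The 25% is a maximum for a single patient on one of two readings, and applies only where scheduling needs the whole allowance.
- **A reader might infer that the arms' SAE percentages cannot be compared at all.** That goes too far. The distortion from this source is bounded, is smaller than sampling error at the planned size, and sits in descriptive tables without hypothesis tests.
- **Termination and early leaving.** SAP 4 reports that the trial was terminated. If follow-up ended on one calendar date, which the documents do not say, delayed patients would gain no extra time. Patients who discontinue have an early final visit, but nothing in the documents shows that this differs by arm. Both points make the size less certain, and both are reasons to report observation time.

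**Conclusion.** The point holds as a bounded, correctable bias together with a conflict between the documents. Under the SAP window, delayed starts push the SAE and AESI percentage upward in the rehabilitation arm only. The per-patient maximum ratio of time at risk is 1.125 or 1.25. At an assumed 20% risk with equal constant hazards, the percentage would be at most 22.2% or 24.3% against 20%, and only if every rehabilitation patient had the full delay.

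The arm-average effect is smaller and cannot be derived from the documents. These figures also assume completed follow-up, which termination may have altered in either arm. The documents support presenting the percentages with observation time beside them; they do not support dismissing the comparison.

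**What to change.** 1. Reconcile Protocol 7.3.4 with SAP 6.1, 7.8 and 7.8.1. For SAEs and AESIs, define one window that starts at randomisation in both arms and ends at Visit 7 or last contact.
2. Report observation time from randomisation by arm.
3. In that same window, add the number of subjects with a first SAE or AESI per 100 patient-years, with a 95% CI. Numerator and denominator must share the window: the SAP assigns events during a nintedanib interruption, or after the last intake, to other periods in the listings, so its on-treatment events should not be divided by total observation time.
4. Add the percentage with an event by day 169 after randomisation, the same cut-off in both arms. Subjects who leave earlier remain in this denominator, which is why the rate should stand beside it.

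The cost is revised SAP wording, a small amount of extra tabulation, and a second event window alongside the nintedanib-based one. Visit dates and event onset dates are already required in the source records and CRF (Protocol 8.3.1), so no new data are needed.

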7.3.4 Safety analyses

Analysis of adverse events will be restricted to nintedanib-related serious adverse events, nintedanib-non-related serious adverse events and events of special interest.

Adverse events will be coded using the Medical Dictionary for Drug Regulatory Activities (MedDRA). Standard BI summary tables and listings will be produced. Adverse events with an onset between start of pulmonary rehabilitation treatment and end of trial will be assigned to the on-treatment period for evaluation. All randomized patients will be included in the safety analysis. In general, safety analyses will be descriptive in nature and will be based on BI standards. No hypothesis testing is planned.

Frequency, severity, and causal relationship of adverse events will be tabulated by system organ class and preferred term after coding according to the current version of the Medical Dictionary for Drug Regulatory Activities at the database lock.

Vital signs, physical examinations, or other safety-relevant data observed at screening, baseline, during the course of the trial and at the end-of-trial evaluation will be assessed with regard to possible changes compared to findings before start of pulmonary rehabilitation.

Analysis of laboratory data and electrocardiogram is not planned.

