4. CHANGES IN THE PLANNED ANALYSIS OF THE STUDY

In writing the core TSAP, these corrections were made to the specifications of the initial TSAP:

1. Important protocol deviation (IPD) E1 in Section 6.2 “No post-baseline 6 MWT assessments” was clarified to E1 “No post-baseline 6 MWD assessments at 12 weeks” and E2 “No baseline 6 MWD assessments” to reflect the primary outcome being measured at 12 week visit.
2. iPD D2 in Section 6.2 was changed from “Discontinued nintedanib” to “Discontinued nintedanib before 12 week visit” to reflect the primary outcome being measured at 12 week visit.
3. The Screening trial period in Section 6.1 was changed from “informed consent to randomization” to “first informed consent to randomization” to account for re-consenting of patients.
4. The trial periods defined in Section 6.1 was clarified to make the distinction between efficacy analysis and safety analysis.

Following termination of the trial, limited efficacy analysis will be performed for an abbreviated CTR. Primary and secondary endpoints will be limited to descriptive outcome measures. Further endpoints will not be done.

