6. GENERAL ANALYSIS DEFINITIONS

6.1 TREATMENT(S)

For treatment specifications, see Section 4 of the CTP.

The following trial periods will be defined with respect to efficacy analyses: Screening, Post-randomization, Treatment, Post-treatment.

- Screening: from first informed consent to randomization
- Post-randomization: from randomization to day of first pulmonary rehabilitation (for those randomized to Pulmonary Rehabilitation Treatment group)
- Treatment:
 - For patients randomized to the Non-Pulmonary Rehabilitation Treatment group: from randomization to the visit 7 end-of-trial visit
 - For patients randomized to the Pulmonary Rehabilitation Treatment group: from first day of pulmonary rehabilitation to the visit 7 end-of-trial visit
- Post-treatment: after the visit 7 end-of-trial visit

Efficacy analyses is independent of nintedanib usage: any dose interruption or discontinuation has no effect on the efficacy analyses. Efficacy analyses will be done on the Post-randomization and Treatment Periods.

The following trial periods will be defined with respect to safety analyses:

Note: the last day of each of the following periods is excluded.

- Screening: from first informed consent to randomization
- Post-randomization: from randomization to day of first Nintedanib drug intake on/after randomization. This period only exists if Nintedanib first drug intake on/after randomization occurred at least 1 day after randomization.
- Treatment: from first Nintedanib drug intake on/after randomization (or re-start of nintedanib if interruption) to last Nintedanib drug intake (or the day before start date of interruption if interruption) plus one day.
- Off-treatment^a: From the start date of Nintedanib interruption to re-start of Nintedanib treatment.
- Residual-effect^a: From the last Nintedanib drug intake plus one day to last Nintedanib trial drug intake plus 28 days plus one day.
- Post-treatment^a: From last trial drug intake plus 29 days. Note, this period is only created if last Nintedanib intake plus 29 days took place before trial completion.
- Post-study: from the latest of last trial drug intake plus 29 days or date of trial completion plus 1 day

^a Note: This period is optional insofar as it does not necessarily exist for all patients.

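### SAP 7.8.1 ends the adverse-event window 28 days after last nintedanib intake, whereas protocol 7.3.4 runs it to end of trial, so some collected SAEs would probably be missing from the by-arm tables

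*SAP*

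**What the plan says.** Protocol 7.3.4: "Adverse events with an onset between start of pulmonary rehabilitation treatment and end of trial will be assigned to the on-treatment period for evaluation". All randomised patients are in the safety analysis.

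SAP 7.8 says the safety analysis is carried out as the protocol defines it, on the Randomised Set, and goes on to name the event types covered. It does not mention the window.

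SAP 7.8.1 bases the analysis on treatment-emergent events and sets a different window: "all adverse events occurring between first nintedanib intake on/after randomization till 28 days after last nintedanib intake will be assigned to the treatment period". It then says that "all adverse events occurring after last nintedanib intake will be assigned to 'residual effect', 'post-treatment' or 'post-study' (for listings only"). The tables are by arm: "The frequency of subjects with AEs will be summarised by treatment, primary system organ class and PT", with a separate table for SAEs.

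For the definition of treatment, 7.8.1 sends the reader elsewhere: "For details on the treatment definition, see Section 6.1". There the safety periods include "Treatment: from first Nintedanib drug intake on/after randomization (or re-start of nintedanib if interruption) to last Nintedanib drug intake", and the following 28 days form a separate residual-effect period. Section 6.1 also provides a post-treatment period, created only when last intake plus 29 days falls before trial completion.

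Under protocol 5.2.6.2, SAEs, AESIs and non-serious adverse drug reactions are collected from consent to end of study, whatever the nintedanib status.

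**The concern.** The two documents give different ends for the same window, and the SAP's end depends on something that was not randomised. Protocol 1.4 says this is not a trial of a drug intervention, and protocol 4.1.1 describes a comparison of pulmonary rehabilitation (PR) with standard care in patients already taking nintedanib. A by-arm SAE table should therefore describe what happened after randomisation to PR or no PR. Under SAP 7.8.1 a patient's window instead closes according to when background therapy stopped, a post-randomisation event that could differ between arms.

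The denominator does not shrink to match. Patients who stop nintedanib stay in the Randomised Set, and SAP 6.1 says stopping has no effect on the efficacy analyses. A patient's week-24 walk distance could thus be summarised while an SAE from the same weeks is missing from the safety table.

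**Working it through.** **Step 1: compare the windows.**

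| | Protocol 7.3.4 | SAP 7.8.1 |
|---|---|---|
| Start | Start of PR | First nintedanib intake on or after randomisation |
| End | End of trial | 28 days after last nintedanib intake |
| Defined for controls? | Start is not: they have no PR | Yes |

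The SAP's start is the better one. It gives controls a start date and covers the wait before PR. The difficulty is the end.

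**Step 2: who is affected.** For a patient still on nintedanib at Visit 7, the SAP window runs past that visit and nothing is lost. A gap arises only if the patient stops for good more than 28 days before the last visit and stays in the trial. The SAP allows for this: deviation D2 covers stopping nintedanib before the 12-week visit, no patient is excluded for a deviation, and the post-treatment period of 6.1 exists only when it begins before trial completion.

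**Step 3: length of the gap for one such patient.** Inputs: L is the day of last intake, counted from randomisation; the 28 days come from SAP 7.8.1; Visit 7 is on day V = 169 (protocol Flow Chart). The window's last day is L + 28, so

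days outside = max(0, V − (L + 28)).

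| Last intake, day L | Calculation | Days outside |
|---|---|---|
| 22 | 169 − 50 | 119 |
| 43 | 169 − 71 | 98 |
| 85 | 169 − 113 | 56 |
| 127 | 169 − 155 | 14 |
| 141 or later | 169 − 169 or less | 0 |

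With the protocol's end of trial as the cut-off, every entry is 0.

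**Step 4: sensitivity to the visit date.** These figures are not upper limits. Protocol 6.2.2 allows up to 6 weeks' extension before PR starts, with later visits moved accordingly. On the longest reading (42 added days, an assumption) Visit 7 falls on day 169 + 42 = 211, and the first four gaps become 161, 140, 98 and 56 days. Follow-up cut short by termination of the trial makes them smaller.

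**Step 5: arm level, illustration only.** The documents give no rate of nintedanib stopping. Assume that stops are spread evenly over days 1 to 169 and that all who stop stay to day 169. The mean gap per stopper is (140 + 139 + … + 1)/169 = 9870/169 = 58.4 days, or 34.6% of 169. If 5% to 20% of an arm stop (assumed), the share of planned follow-up outside the window is 0.05 × 34.6% = 1.7% to 0.20 × 34.6% = 6.9%. These are shares of days, not of events.

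**The case against.** Several counter-arguments stand in whole or part.

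- **The exclusion is inferred.** It follows from the treatment-emergent basis and the listings-only remark. For further detail on summarising events, 7.8.1 refers to a sponsor guideline that is not among the documents. The natural reading still leaves late events out of the tables, and nothing in the SAP says otherwise.
- **Few patients may be affected.** Protocol 4.1.2 requires nintedanib throughout. Some who stop will leave under protocol 3.3.4.1 with an early Visit 7; if that visit falls within 28 days of last intake, nothing is lost. But protocol 3.3.4 asks sites to keep patients in the trial.
- **A nintedanib-based window has a purpose.** Both documents classify SAEs by relation to nintedanib. That supports keeping it as a second display, not as the only basis for comparing PR with no PR.
- **The stakes are limited.** The trial was terminated, safety is descriptive with no test, and all events are listed. However, the reductions announced in SAP Section 4 concern efficacy and further endpoints; the adverse-event tables remain planned.

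A reader might infer two stronger points that the documents do not support. The first is that SAP Section 4 conceals the departure. That section says "these corrections were made to the specifications of the initial TSAP", so it is not a list of departures from the protocol, and the initial plan is not available to check. Its fourth item reads "The trial periods defined in Section 6.1 was clarified to make the distinction between efficacy analysis and safety analysis". One can say only that the text at hand does not mention the difference from protocol 7.3.4.

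The second is that the tables also lose events during temporary interruptions and in the 28 days after last intake, because 6.1 splits its Treatment period there. But 7.8.1 assigns those 28 days to the treatment period and ties the finer labels to the listings. The two sections can be read as table window versus listing labels; the wording is unclear rather than clearly wrong.

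**Conclusion.** The conflict is in the text and should be corrected. Protocol 7.3.4 and SAP 7.8 point to end of trial, while SAP 7.8.1 stops at last nintedanib intake plus 28 days. Read naturally, 7.8.1 removes some collected SAEs and AESIs from the by-arm tables in either arm, according to a post-randomisation event, with the Randomised Set denominator unchanged.

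The effect is limited. It reaches only patients who stop nintedanib for good more than 28 days before their last visit and remain in the trial. For such a patient the uncovered time runs from 14 days (last intake on day 127) to 119 days (day 22), given Visit 7 on day 169. The number of such patients, and so the number of events, cannot be derived from the documents, and the arm-level range of 1.7% to 6.9% is no better than its assumed stopping rates. It should not be inferred that many SAEs would be lost or that any test result would change.

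**What to change.** - Tabulate SAEs and AESIs by randomised arm on the Randomised Set, with onset from randomisation to each patient's Visit 7 or trial completion, regardless of when PR starts or whether nintedanib is interrupted or stopped. Use a per-patient end, because protocol 8.6 defines end of trial as the last patient's last visit.
- Show follow-up time by arm, since a delayed PR start can move Visit 7 later in the PR arm.
- Keep the nintedanib-based window with its 28 days as a supplementary table or listing.
- State in SAP 6.1 and 7.8.1 which span the tables use and which labels serve only the listings.
- Note in the SAP that the window differs from protocol 7.3.4.

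The cost is one extra table and some SAP wording. The data are already collected, so nothing changes for sites or patients.

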3. DESCRIPTION OF DESIGN AND TRIAL POPULATION

3.1 OVERALL TRIAL DESIGN AND PLAN

This is a Phase IV, multi-centre, prospective, randomised, open label clinical trial to investigate the effect of pulmonary rehabilitation in patients with IPF currently treated with nintedanib at a dose of 150 mg bid for up to 30 months.

A total of approximately 290 patients with confirmed IPF diagnosis, already using nintedanib will be randomised, 145 in active arm and 145 in the control group. [REDACTED]

After a screening visit, if the patient complies with all inclusion and exclusion criteria and provides informed consent, randomisation will be performed by phone or Internet, using an Interactive phone/web Response System (IRT). Patients will then enter the treatment phase for 24 weeks. The treatment phase consists of 12 weeks of pulmonary rehabilitation for those patients randomized to that arm, to take place during the first 12 weeks of the treatment phase.

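### SAP 6.1 and 7.8.1 cut every safety period by nintedanib intake, so SAEs arising in the 12 weeks of rehabilitation are never summarised apart from the 12 weeks after it

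*SAP*

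**What the plan says.** Protocol 3.1 sets the design: "Patients will then enter the treatment phase for 24 weeks". On the intervention it says: "The treatment phase consists of 12 weeks of pulmonary rehabilitation for those patients randomized to that arm, to take place during the first 12 weeks". Protocol 4.1.1 says that no study medication is included, so rehabilitation is the only randomised difference.

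The safety periods follow a different clock. SAP 6.1 gives "Treatment: from first Nintedanib drug intake on/after randomization (or re-start of nintedanib if interruption) to last Nintedanib drug intake", and its off-treatment, residual-effect and post-treatment periods are likewise cut by nintedanib intake. SAP 7.8.1 repeats the principle for adverse events: "all adverse events occurring between first nintedanib intake on/after randomization till 28 days after last nintedanib intake will be assigned to the treatment period".

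For the tables, SAP 7.8.1 says: "The frequency of subjects with AEs will be summarised by treatment, primary system organ class and PT". It adds: "All analyses of AEs will be based on the number of subjects with AEs and NOT on the number of AEs". No table is divided at Visit 5 or at the end of rehabilitation.

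Protocol 7.3.4 uses a third clock: "Adverse events with an onset between start of pulmonary rehabilitation treatment and end of trial will be assigned to the on-treatment period". SAP 7.8 nevertheless says that the safety analysis is performed as the protocol defines it.

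**The concern.** A safety table for this trial should help a reader judge whether rehabilitation causes serious events. The arms differ by scheduled treatment only while rehabilitation is running. From Visit 5 to Visit 7 neither arm is scheduled for it, yet both halves go into one count per arm.

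Little else in the plan would pick up the signal. The analysed events are SAEs, split by relation to nintedanib, and two drug-oriented AESIs (liver injury and gastrointestinal perforation). Relatedness is judged against the drug, and no summary by relation to rehabilitation is planned. That leaves arm and timing. Protocol 4.2.1.2 foresees adverse events related to rehabilitation, and Appendix 10.1.1 lists cardiac and musculoskeletal complications of exercise challenges.

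The efficacy endpoints are separated at weeks 12 and 24, and SAP 6.1 makes them independent of nintedanib use. Safety has neither feature. An SAE during rehabilitation in a patient who stopped nintedanib more than 28 days earlier would fall outside the treatment period.

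**Working it through.** **Plan's own figures.** The documents give no SAE rate and no safety power. The only design figure is for the walk distance: n per arm = 2(1.96 + 0.842)² × (85/30)² ≈ 126.0, rounded up to 127, or 254 in total, as Protocol 7.7 states (the t-test solution is 126.99). Only the planned 145 per arm (Protocol 3.1) is used below.

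**Assumptions.** Constant background hazard; rehabilitation multiplies it by 2 during its 12 weeks only; equal follow-up; 24-week background risk b from 5% to 30%.

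**Formulas.** Cumulative hazard per 12 weeks: L = −ln(1 − b)/2.
- Control: 1 − exp(−L) over 12 weeks, 1 − exp(−2L) over 24.
- Rehabilitation arm: 1 − exp(−2L) over 12 weeks, 1 − exp(−3L) over 24.
- z = risk difference / √[(p₁(1 − p₁) + p₂(1 − p₂))/145]. This only gauges visibility, since no safety test is planned.

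**At b = 20%**, L = 0.2231/2 = 0.1116.
- Rehabilitation weeks: 10.6% vs 20.0%; ratio 1.89, difference 9.4 points, z = 2.25.
- Pooled 24 weeks: 20.0% vs 28.4%; ratio 1.42, difference 8.4 points, z = 1.69.

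| b | Ratio, 12 wk → 24 wk | Difference (points) | z |
|---|---|---|---|
| 5% | 1.97 → 1.48 | 2.5 → 2.4 | 1.11 → 0.85 |
| 10% | 1.95 → 1.46 | 4.9 → 4.6 | 1.57 → 1.20 |
| 20% | 1.89 → 1.42 | 9.4 → 8.4 | 2.25 → 1.69 |
| 30% | 1.84 → 1.38 | 13.7 → 11.4 | 2.79 → 2.05 |

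z falls by about a quarter throughout (1.69/2.25 = 0.75). That proportion does not depend on the number per arm, because n cancels.

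**Effect of the scheduling delay.** Protocol 6.2.2 and flow chart footnote 6 let the interval between Visits 2 and 3 be extended by up to 6 weeks so that rehabilitation can be scheduled; later visits move with it. Taking the full 6 weeks, in the rehabilitation arm only, and **no harm at all**, at b = 20%:
- Whole period, 30 vs 24 weeks: 1 − exp(−2.5L) = 24.3% vs 20.0%, a spurious ratio of 1.22 (1.24 to 1.20 for b = 5% to 30%).
- Visit 2 to Visit 5, 18 vs 12 weeks: 1 − exp(−1.5L) = 15.4% vs 10.6%, a spurious ratio of 1.46 (1.49 to 1.44).

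So crude counts are distorted by follow-up length, and a split starting at randomisation in both arms would make this worse. Starting the phase on the first rehabilitation day gives about 12 weeks in each arm. Under these assumptions, events per person-week give a ratio of 1 when there is no harm, whatever the delay.

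**The case against.** Several stronger readings are tempting, and the documents do not support them.

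- **That the 24-week table is biased towards no difference.** It is not. Cumulative risk by randomised arm over 24 weeks is a legitimate quantity, and full follow-up suits a trial that asks whether effects endure. The risk difference is close to that of the rehabilitation weeks, especially when SAEs are uncommon. The delay pushes the crude ratio upwards, so the net direction is not fixed.
- **That all SAEs are pooled into one period.** SAP 6.1 and 7.8.1 send events before first intake and after the window to other periods, and label events during interruptions as off-treatment in the listings. The point is that all these periods are cut by nintedanib intake.
- **That early and late harm cannot be told apart.** Protocol 7.3 lists all individual data and 8.3.1 makes AE onset dates mandatory. Timing can be recovered case by case; what is missing is a summary by arm.
- **That a z of 2.25 would have been reached.** It assumes 145 per arm, whereas SAP section 4 says the trial was terminated and the documents do not give the number enrolled.

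Two further objections have some force. The protocol's own on-treatment period also runs to the end of the trial, so the SAP did not drop a split that the protocol had promised. And SAP 7.8.1 refers to an internal sponsor guideline for AE presentation that is not available here, so time-based displays cannot be wholly excluded. Neither puts a rehabilitation-phase summary into the plan as written.

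**Conclusion.** The point holds as a modest one. Because the safety periods follow nintedanib and the tables have no phase split, an SAE excess confined to rehabilitation is less visible as a ratio and relative to noise: 1.9 becomes 1.4 at an assumed 20% background and doubled hazard, and z falls by about a quarter across backgrounds of 5% to 30%. The risk difference loses 0.1 to 2.3 points over the same range. These sizes rest on an assumed SAE rate, an assumed hazard ratio, no excess after rehabilitation stops, and equal follow-up.

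The conflicting start of the period is a separate matter and needs no assumption. Protocol 7.3.4 starts at rehabilitation, which is undefined for controls. SAP 7.8.1 starts at nintedanib intake while SAP 7.8 claims to follow the protocol.

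**What to change.** In SAP 7.8.1, keep the overall column by randomised arm and add SAE and AESI summaries by arm, regardless of nintedanib interruption or discontinuation, for:

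1. the rehabilitation phase: first rehabilitation day to Visit 5, and randomisation to Visit 5 in controls;
2. Visit 5 to Visit 7.

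Show events between randomisation and the first rehabilitation day separately. Give person-time and exposure-adjusted rates beside the counts. State how patients who never start rehabilitation or miss Visit 5 are handled; the former remain in the overall column in any case. Reconcile the on-treatment period in Protocol 7.3.4 with SAP 7.8.1 and record the choice in SAP section 4.

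The cost is SAP wording and a few table columns, built from onset dates, visit dates and rehabilitation records already collected. The downside is smaller counts per cell, more so after early termination, so the phase summaries may be more useful for total SAEs and AESIs than for every preferred term.
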